7.6.7 Select Adverse Events

Unless otherwise specified, analyses will be performed by select AE category. Some analyses may also be repeated by subcategory of endocrine events (APPENDIX 1).

7.6.7.1 Incidence of select AE

See Core Safety SAP.

Select AEs will be summarized for all treated subjects by treatment arms for each category/subcategory:

- Overall summary of any select AEs by worst CTC grade presented by Category or Subcategory/PT (any grade, grade 3-4, grade 5)
- Overall summary of drug-related select AEs by worst CTC grade presented by Category or Subcategory/PT (any grade, grade 3-4, grade 5)
- Overall summary of any select Endocrine AEs by worst CTC grade presented by Category or Subcategory/PT (any grade, grade 3-4, grade 5)
- Overall summary of drug-related Endocrine select AEs by worst CTC grade presented by Category or Subcategory/PT (any grade, grade 3-4, grade 5)
- Overall summary of any serious select AEs by worst CTC grade presented by Category or Subcategory /PT (any grade, grade 3-4, grade 5)
- Overall summary of drug-related serious select AEs by worst CTC grade presented by Category or Subcategory /PT (any grade, grade 3-4, grade 5)
- Overall summary of any serious select Endocrine AEs by worst CTC grade presented by Category or Subcategory /PT (any grade, grade 3-4, grade 5)
- Overall summary of drug-related serious select Endocrine AEs by worst CTC grade presented by Category or Subcategory /PT (any grade, grade 3-4, grade 5)
- Overall summary of select AEs leading to discontinuation by worst CTC grade presented by Category or Subcategory/PT (any grade, grade 3-4, grade 5)
- Overall summary of drug-related select AEs leading to discontinuation by worst CTC grade presented by Category or Subcategory/PT (any grade, grade 3-4, grade 5)
- Overall summary of any select Endocrine AEs leading to discontinuation by worst CTC grade presented by Category or Subcategory/PT (any grade, grade 3-4, grade 5)
- Overall summary of drug-related select Endocrine AEs leading to discontinuation by worst CTC grade presented by Category or Subcategory/PT (any grade, grade 3-4, grade 5)

The analyses will be conducted using the 30-day safety window.

By-subject select AE listing will be provided.

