### 3. Age and Reproductive Status

- a) Males and Females,  $\geq 18$  years of age.
- b) Women of childbearing potential (WOCBP) must have a negative serum or urine pregnancy test (minimum sensitivity 25 IU/L or equivalent units of HCG) within 24 hours prior to the start of study drug.
- c) Women must not be breastfeeding.
- d) WOCBP must agree to follow instructions for method(s) of contraception for the duration of treatment with nivolumab plus 5 half-lives of nivolumab plus 30 days (duration of ovulatory cycle) for a total of 5 months post-treatment completion.
- e) Males who are sexually active with WOCBP must agree to follow instructions for method(s) of contraception for the duration of treatment with nivolumab plus 5 half-lives of nivolumab plus 90 days (duration of sperm turnover) for a total of 7 months post-treatment completion. In addition, male subjects must be willing to refrain from sperm donation during this time.

- f) Azoospermic males are exempt from contraceptive requirements. WOCBP who are continuously not heterosexually active are also exempt from contraceptive requirements, and still must undergo pregnancy testing as described in this section.

See [Appendix 3](#) for Women of Childbearing Potential Definitions and Methods of Contraception.

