### **6.2.1 Nonserious Adverse Event Collection and Reporting**

The collection of nonserious AE information should begin at initiation of study drug. Nonserious AE information should also be collected from the start of a placebo lead-in period or other observational period intended to establish a baseline status for the subjects.

Nonserious AEs should be followed to resolution or stabilization, or reported as SAEs if they become serious (see [Section 6.1.1](#)). Follow-up is also required for nonserious AEs that cause interruption or discontinuation of study drug and for those present at the end of study treatment as appropriate. All identified nonserious AEs must be recorded and described on the nonserious AE page of the CRF (paper or electronic).

Completion of supplemental CRFs may be requested for AEs and/or laboratory abnormalities that are reported/identified during the course of the study.

All nonserious adverse events (not only those deemed to be treatment-related) should be collected continuously during the treatment period and for a minimum of 100 days following discontinuation of study treatment.

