2.1 Study Design

This is an open-label, randomized phase IIIb/IV dose frequency optimization trial in adult patients with advanced/metastatic (Stage IIIb/IV) NSCLC (non-Sq and Sq). Subjects will have received approximately up to 12 months (52 weeks) of nivolumab therapy at either 3 mg/kg or 240 mg every 2 weeks and achieved a complete response (CR), partial response (PR), or stable disease (SD) as evidenced by 2 consecutive tumor assessments prior to enrollment. At enrollment, subjects will be randomized 1:1 to receive either 240 mg every 2 weeks (Arm 1) or 480 mg every 4 weeks (Arm 2). Randomization will be stratified by histology (Sq vs. Non-Sq) and response criteria to pre-study nivolumab at randomization (CR or PR vs. SD). For subjects receiving nivolumab 240 mg every 2 weeks, each 14-day dosing period will constitute a cycle. For subjects receiving nivolumab 480 mg every 4 weeks, each 28-day dosing period will constitute a cycle.

Subjects will continue treatment until disease progression or unacceptable toxicity for a maximum of 2 years from first randomized dose. The follow-up period begins when the decision to permanently discontinue a subject from study therapy is made (no further treatment or retreatment with nivolumab is anticipated). All subjects who discontinue study drug should comply with protocol specified follow-up procedures as outlined in Section 5 of the Clinical Protocol until death or the conclusion of the study. The only exception to this requirement is when a subject withdraws consent for all study procedures including post-treatment study follow-up or loses the ability to consent freely.

The study design schematic is presented in [Figure 2.1-1](#).

Figure 2.1-1: Study Schema

Each patient’s last study visit will be defined as the last on-treatment or follow-up visit that occurs prior to the date of 3 years after the initiation of randomized therapy. The study will be completed no later than 3 years after the last subject’s first visit.

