6.1.2 Post baseline period

On-treatment AEs will be defined as AEs with an onset date-time on or after the date-time of the first dose of study treatment (or with an onset date on or after the day of first dose of study treatment if time is not collected or is missing). For subjects who are off study treatment, AEs will be counted as on-treatment if the events occurred within 100 days of the last dose of study treatment, unless otherwise specified.

On-treatment evaluations (laboratory tests, pulse oximetry and vital signs) will be defined as evaluations taken after the day (and time, if collected and not missing) of first dose of study treatment. For subjects who are off study treatment, evaluations should be within 100 days of the last dose of study treatment.

Post-treatment AEs will be defined as AEs with an onset date-time 100 days after last dose of study treatment.

Late emergent drug related AEs will be defined as drug related AEs with an onset date greater than 100 days after the last dose of study treatment in subjects off study treatment.

Post-treatment evaluations, if necessary, will be defined as evaluations taken 100 days after last dose of study treatment.

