7.6.4 Adverse Events Leading to Dose Delay

AEs leading to dose delay will be summarized for all treated subjects by treatment arm:

- Overall summary of AEs leading to dose delay by worst CTC grade (grade 1, 2, 3, 4, 5, unknown) presented by SOC/PT

The analysis will be conducted using the 30-day safety window and repeated using the 100-day safety window.

By-subject listing of AEs leading to dose delay will be provided.

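### Select adverse events are tabulated only to 30 days after the last dose, although AEs are collected to day 100 and 100 days is the SAP's default window

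*SAP*

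**What the plan says.** SAP 7.6.7.1 (incidence of select AEs) states: "The analyses will be conducted using the 30-day safety window". Sections 7.6.7.2 (time to onset) and 7.6.7.3 (time to resolution) say the same. So do the select-AE part of 7.6.9 (immune-modulating medication) and the select-AE table of 7.6.10 (subjects with one or several events). None gives a reason or asks for a 100-day repeat.

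Elsewhere the plan looks further:

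- The SAP 6.1.2 default for subjects off treatment is: "AEs will be counted as on-treatment if the events occurred within 100 days of the last dose of study treatment, unless otherwise specified".
- Under Protocol 6.2.1, nonserious AEs are to be "collected continuously during the treatment period and for a minimum of 100 days following discontinuation of study treatment". Protocol 6.1.1 collects SAEs over the same 100 days.
- SAP 7.6.4, on AEs leading to dose delay, uses both windows: "The analysis will be conducted using the 30-day safety window and repeated using the 100-day safety window". The grade-shift table in 7.6.5 and the all-AE occurrence rates in 7.6.10 also use both.
- Immune-mediated AEs (IMAEs, 7.6.6), other events of special interest (7.6.8) and the AE subgroup tables (7.6.16) use 100 days.

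**The concern.** Protocol 1.4.2 describes select AEs as events of special clinical interest, and comparing safety between the two schedules is a secondary objective. Among the AE analyses whose window this SAP states, only those of select AEs stop at day 30 with no repeat. A select AE starting on day 45 after the last dose is collected and counts as on-treatment by the SAP's own default, but it does not enter the tables built for that kind of event. What is at stake is how complete the by-arm select-AE summary is, and whether it can be read alongside the 100-day tables for IMAEs and special-interest events.

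**Working it through.** **1. How much follow-up is dropped.** AEs are collected to day 100, and Protocol Table 5.1-3 places Follow-up Visit 1 near day 30 and Visit 2 about 70 days later (30 + 70 = 100). A 30-day window drops 100 − 30 = 70 of those 100 days.

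**2. Whether other 100-day tables fill the gap.**

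| Table | Window | Covers select AEs on days 31–100? |
|---|---|---|
| Select AEs (7.6.7, parts of 7.6.9 and 7.6.10) | 30 days | No |
| IMAEs (7.6.6) | 100 days | Only with no clear alternate cause and, outside the listed endocrine events, only if treated with immune-modulating medication |
| Other events of special interest (7.6.8) | 100 days | Only six rare categories, such as myasthenic syndrome and uveitis |
| Grade shift (7.6.5), all-AE rates (7.6.10) | Both | Yes, but not by select-AE category |
| Drug-related AEs by subgroup (7.6.16) | 100 days | If drug-related; by organ class and preferred term, not by select-AE category |

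An untreated hepatic, renal or skin select AE on day 45 would therefore appear in no select-AE or IMAE summary.

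**3. Why days 31 to 100 are not empty time.**

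- Contraception for women runs for treatment "plus 5 half-lives of nivolumab plus 30 days (duration of ovulatory cycle) for a total of 5 months". With 30-day months, the implied half-life is (150 − 30)/5 = 24 days. Assuming first-order elimination, 0.5^(30/24) = 0.42 of the concentration remains at day 30 and 0.5^(100/24) = 0.06 at day 100. This rests on rounded contraception periods, not on pharmacokinetic data.
- Follow-up Visit 1 may fall as late as day 35 (30 + 5) or later, so an event whose onset is recorded at that visit can fall outside the window.
- SAP 7.4.2.1 lets a dose be delayed to 6 weeks (42 days). For a subject who never resumes, events on days 31 to 42 fall outside (42 − 30 = 12 days).

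**4. Whether the window treats the arms differently.** The intervals are 14 and 28 days (SAP 2.1). SAP Appendix 1 counts from the last dosing date in both arms.

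| | Arm 1 (Q2W) | Arm 2 (Q4W) | Difference |
|---|---|---|---|
| 30-day window, from last dose | 30 | 30 | 0 |
| 30-day window, past next due dose | 30 − 14 = 16 | 30 − 28 = 2 | 14 |
| 100-day window, past next due dose | 100 − 14 = 86 | 100 − 28 = 72 | 14 |
| 30-day window, mean days after a random stop | 30 − 7 = 23 | 30 − 14 = 16 | 7 |
| 100-day window, mean days after a random stop | 100 − 7 = 93 | 100 − 14 = 86 | 7 |

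The last two rows assume that stopping is uniform within a cycle, so the mean time since the last dose is 7 or 14 days.

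A simulation of 2,000,000 subjects gave both arms the same stop times. These followed a piecewise-exponential curve through the SAP's assumed PFS rates (0.63 at 6 months, 0.48 at 12), capped at 730 days, with treatment stopping at progression and no delayed doses. Arm 2's observation ended 4.9 days earlier on average, or 6.8 days among subjects stopping before the cap. As a share of observed time, 4.9/406.4 = 1.2% with the 30-day window and 4.9/476.4 = 1.0% with the 100-day window. For a 6-month course the share is larger: 7/(180 + 30) = 3.3%.

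**The case against.** There is a fair case for leaving the plan alone.

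- **The choice is permitted.** The 100-day default yields where a section specifies otherwise, and 7.6.7 does. The CA209057 safety table in Protocol 1.4.2 also used 30 days unless stated otherwise, so a 30-day table helps comparison. This stands, and it is why the 30-day table should stay.
- **The Core Safety SAP may already supply a 100-day table.** Sections 7.6.7.1 to 7.6.7.3 all refer to it, and it is not among the documents. This cannot be excluded. However, 7.6.5, 7.6.6.1 and 7.6.8.1 refer to it too and still state their own 100-day window or repeat, so the silence in 7.6.7 reads as 30 days only.
- **The yield may be small.** Protocol 1.4.2 reports that in CA209017 most patients with a treatment-related select AE had it within 3 months of first dose, and subjects here have already tolerated nivolumab. This stands, and the documents give no figure for select AEs starting on days 31 to 100.
- **A later window can pick up events after other therapy begins.** This stands and needs a flag.

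A reader might also infer that the trial misses late events. It does not: they are collected to day 100 and partly reported in the other tables.

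**Conclusion.** As written in this SAP, the select-AE tables omit events with onset on days 31 to 100, which the trial collects and the SAP by default counts as on-treatment. The 100-day IMAE and special-interest tables are narrower and replace them only in part. The gap is one of tabulation, and the number of events affected cannot be worked out from the documents.

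A reader who sees 16 days against 2 might conclude that the 30-day window favours Q4W. The documents do not support that. Both arms have 30 days from the last dose. The difference relative to the next due dose or the stop date comes from the Q2W and Q4W intervals, and its absolute size is the same at 100 days. It is at most 14 days and about 7 on average, roughly 1% to 3% of observed time, if stop times are equal in both arms and no doses are delayed. This is an optional improvement, subject to what the Core Safety SAP contains.

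**What to change.** 1. In SAP 7.6.7.1, 7.6.7.2, 7.6.7.3, the select-AE part of 7.6.9 and the select-AE table of 7.6.10, keep the 30-day analysis and add the 100-day repeat in the form already used in 7.6.4. If the Core Safety SAP already provides it, cite that explicitly. The time-to-onset censoring rule in Appendix 1 already allows for either window.
2. In the 100-day tables, flag events with onset after the start of subsequent anti-cancer therapy.
3. Add exposure-adjusted select-AE rates by arm, as 7.6.10 already plans for all AEs, to deal with the small difference in observed time that a longer window leaves in place.

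The cost is extra output from data already collected, with no new visits or data. The drawback is that some events on days 31 to 100 may reflect later therapy, hence the flag.

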7.6.7.2 Time-to onset of select AE

See Core Safety SAP.

Time-to onset of the following specific events will be summarized for each category/subcategory of select AEs by treatment arm:

- Time-to onset of any grade select AE
- Time to onset of grade 3 to 5 select AE
- Time to onset of any grade drug-related select AE
- Time to onset of grade 3 to 5 drug-related select AE
- Time-to onset of any grade select endocrine AE
- Time to onset of grade 3 to 5 select endocrine AE
- Time to onset of any grade drug-related select endocrine AE
- Time to onset of grade 3 to 5 drug-related select endocrine AE

The median time-to onset and range summary statistics will be reported.

Additional details regarding the time-to onset definition and censoring rules are described in time-to onset definition subsection of [APPENDIX 1](#).

The analyses will be conducted using the 30-day safety window.

7.6.7.3 Time-to resolution of select AE

See Core Safety SAP.

Time to resolution of the following specific events will be summarized separately for each category/subcategory by treatment arm:

- Time-to resolution of any grade select AE
- Time-to resolution of grade 3 to 5 select AE
- Time-to resolution of any grade drug-related select AE
- Time-to resolution of grade 3 to 5 drug-related select AE
- Time-to resolution of any grade select AE where immune modulating medication was initiated by category
- Time-to resolution of grade 3 to 5 select AE where immune modulating medication was initiated by category
- Time-to resolution of any grade drug-related select AE where immune modulating medication was initiated by category
- Time-to resolution of grade 3 to 5 drug-related select AE where immune modulating medication was initiated by category
- Time-to resolution of any grade select endocrine AE
- Time-to resolution of grade 3 to 5 select endocrine AE
- Time-to resolution of any grade drug-related select endocrine AE

- Time-to resolution of grade 3 to 5 drug-related select endocrine AE
- Time-to resolution of any grade select endocrine AE where immune modulating medication was initiated by subcategory
- Time-to resolution of grade 3 to 5 select endocrine AE where immune modulating medication was initiated by subcategory
- Time-to resolution of any grade drug-related select endocrine AE where immune modulating medication was initiated by subcategory
- Time-to resolution of grade 3 to 5 drug-related select endocrine AE where immune modulating medication was initiated by subcategory

Time-to resolution analyses are restricted to treated subjects who experience the specific events. Time-to resolution where immune modulating medication is initiated analyses are restricted to treated subjects who experience the specific events and who receive immune modulating medication during the longest select AE.

The following summary statistics will be reported: percentage of subjects who experience the specific events, percentage of subjects with resolution of their select AE of longest duration, median time-to resolution (derived from Kaplan-Meier estimation) and ranges.

See time-to resolution definition subsection of [APPENDIX 1](#) for additional details.

The analyses will be conducted using the 30-day safety window.

7.6.8 Other Events of Special Interest

Unless otherwise specified, analyses will be performed by other events of special interest category. Other events of special interest include the following categories: Myasthenic Syndrome, Demyelination event, Guillain-Barre Syndrome, Pancreatitis event, Uveitis event, Encephalitis event.

Table 7.6.8-1 below provides a summary of the other events of special interest category and their respective PTs.

Table 7.6.8-1: Preferred Terms Included in Analysis of Other Events of Special Interest

Other Events of Special Interest Category	Preferred Terms included under Other Events of Special Interest Category
Myasthenic Syndrome	Myasthenia Gravis, Myasthenia Gravis Crisis, Myasthenic Syndrome
Demyelination Event	Autoimmune demyelinating Disease, Demyelination
Guillain-Barre Syndrome	Guillain-Barre Syndrome, Miller Fisher Syndrome
Pancreatitis Event	Autoimmune pancreatitis, Haemorrhagic Necrotic Pancreatitis, Pancreatitis, Pancreatitis Acute, Pancreatitis Necrotising

Table 7.6.8-1: Preferred Terms Included in Analysis of Other Events of Special Interest

Other Events of Special Interest Category	Preferred Terms included under Other Events of Special Interest Category
Uveitis Entve	Autoimmune Uveitis, Chorioretinitis, Cyclitis, Iridocyclitis, Iritis, Uveitis
Encephalitis Event	Acute Encephalitis with refractory, Repetitive Partial Seizures, Bickerstaff’s Encephalitis, Encephalitis, Encephalitis Allergic, Encephalitis Autoimmune, Encephalitis Brain Stem, Encephalitis Haemorrhagic, Encephalitis Lethargica, Encephalitis Toxic, Lupus Encephalitis, Noninfective Encephalitis, Panencephalitis, Rasmussen Encephalitis, Subacute Sclerosing Panencephalitis

7.6.8.1 Incidence of other events of special interest

See Core Safety SAP.

Other events of special interest will be summarized for all treated subjects by treatment arm:

- Overall summary of other events of special interest by worst CTC grade (grade 1, 2, 3, 4, 5, unknown) presented by Category/PT
- Overall summary of other events of special interest by worst CTC grade (any grade, grade 3-4, grade 5) presented by Category/PT
- Overall summary of drug-related other events of special interest by worst CTC grade (grade 1, 2, 3, 4, 5, unknown) presented by Category/PT
- Overall summary of drug-related other events of special interest by worst CTC grade (any grade, grade 3-4, grade 5) presented by Category/PT.
- Overall summary of serious other events of special interest by worst CTC grade (grade 1, 2, 3, 4, 5, unknown) presented by Category/PT
- Overall summary of other events of special interest leading to discontinuation by worst CTC grade (grade 1, 2, 3, 4, 5, unknown) presented by Category/PT
- Overall summary of other events of special interest that required immune modulating medication by worst CTC grade (grade 1, 2, 3, 4, 5, unknown) presented by Category/PT
- Overall summary of other events of special interest that required immune modulating medication by worst CTC grade (any grade, grade 3-4, grade 5) presented by Category/PT
- Overall summary of drug-related other events of special interest that required immune modulating medication by worst CTC grade (grade 1, 2, 3, 4, 5, unknown) presented by Category/PT

- Overall summary of drug-related other events of special interest that required immune modulating medication by worst CTC grade (any grade, grade 3-4, grade 5) presented by Category/PT

The analyses will be conducted using the 100-day safety window.

By-subject other events of special interest listing will be provided.

7.6.8.2 Time-to onset of other events of special interest

See Core Safety SAP.

Time-to onset of the following other events of special interest will be summarized for each category by treatment arm:

- Time-to onset of any grade other events of special interest
- Time-to onset of grade 3 to 5 other events of special interest
- Time-to onset of any grade drug-related other events of special interest
- Time-to onset of grade 3 to 5 drug-related other events of special interest
- Time-to onset of any grade other events of special interest where immune modulating medication was initiated
- Time-to onset of grade 3 to 5 other events of special interest where immune modulating medication was initiated

The median time-to onset and range summary statistics will be reported.

Additional details regarding the time-to onset definition and censoring rules are described in time-to onset definition subsection of [APPENDIX 1](#).

The analyses will be conducted using the 100-day safety window.

